4.4 Inclusion Criteria for Enrollment as a Plasma Donor

- Age of 18 years or older
- Weight of 110 pounds or greater
- History of confirmed SARS-CoV-2 infection
- At least 21 days post COVID-19 symptom resolution at the time of consent, and at least 28 days post COVID-19 symptom resolution at the time of plasma donation.
- Person has passed the American Red Cross Donor Health Questionnaire
- Person is willing and able to provide written informed consent and comply with all protocol requirements.

4.5 Exclusion Criteria for Plasma Donor

- Female subjects with positive pregnancy test, breastfeeding, or planning to become pregnant/breastfeed during the study period.

- Medical conditions for which plasma donation is not considered safe (presence of a blood borne pathogen, presence of HLA antibodies, etc)
- Other disqualifying condition as set forth by the American Red Cross blood/plasma donation policies.

Inclusion Criteria for Immunologic Controls

1. PBMCs with 5-10 million cryopreserved cells per specimen with 2 timepoints per patient
2. Serum or plasma 500 UI each (2 timepoints from each patient)

Exclusion Criteria for Immunologic Controls

Specimens not available through the COVID Repository protocol.

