8.2 Virologic measures

1. Rates, levels and duration of SARS-CoV-2 RNA in OP or NP swabs and/or subgenomic - messengerRNA (sg-mRNA) from Viral Transport Media (VTM) by RT-PCR at days 0, 4, 7, 14, and 21. Other specimen types may be tested as available (e.g. BAL fluid, tracheal secretions, sputum, etc.) or when RT-PCR assays are validated for additional sources (i.e., stool, blood). VTM will be obtained from the original OP or NP swab collection devices as detailed above. Trial patient samples will be compared to control non-transfused hospitalized patient samples stored in the clinical labs.
2. Serologic positivity and neutralization antibody titers for anti-SARS-CoV-2 at days designated time points at 0, 7, 14, and 28.

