8.3 Immune Evaluations

Immune evaluations (IEs) will be conducted as delineated in **Table 1**. Baseline serum and cells will be aliquoted from the pheresis. Blood draws (4 green top tubes containing approximately 30-40 milliliters of anti-coagulated blood and 1 red top tube containing 8 milliliters of serum) at each time point. Immunologic Control samples from non-transfused hospitalized patients will be obtained from the UVA COVID-19 Biorepository. Permission has been obtained from the Biorepository Committee.

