9.0 STATISTICAL CONSIDERATIONS

9.1 Power calculation

Twenty-nine evaluable patients will have 80% power to declare a significant decrease in ICU admissions from a historical control of 50% of hospitalized patients to 25% with a two-sided type I error of 0.05 (reject ICU admission rate=50% if only 8 or less patients are admitted to ICU among 29 evaluable patients).

Data analysis: For categorical clinical endpoints, frequency with percentage will be summarized. For the quantitative clinical variables and immune response variables measured in this objective, we will produce summary statistics (including means, medians, and standard deviations) for data at pre- and post-CIP infusions. Subsequent analyses will compare the serologic and neutralization antibody titers for anti-SARS-COV-2 antibodies and immune response variables (after a suitable data transformation to improve normal distribution, if necessary) pre- and post-treatment using a paired t-test (or Wilcoxon sign ranked test if the data are not approximately normally distributed). The level of each measured immune biomarker measured at the follow-up time points will be plotted to visually show the change of immune responses over time. To explore whether immune responses at pre- or peak improvement at post-CIP infusions associate with clinical endpoints (such as ICU admission, intubation), logistic regression for binary endpoints and Cox regression for time to event endpoints will be used to analyze each measured immune biomarker respectively. These effects will be compared to biospecimen from non-transfused immunologic controls. Analyses will adjust for other covariates such as age and co-morbidities. No

multiplicity adjustment is planned due to the nature of being exploratory. A two-sided p-value of < 0.05 will be considered significant.

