10.9 Subject Status Definitions

- Enrolled: All subjects who sign an informed consent will be considered enrolled on the study. All subjects consented on the study must be entered into Clinical Trials Office Database.
- Screen Failure: A subject who is withdrawn or discontinues from study screening prior to being on study is considered a screen failure. Screen failures are not considered a study accrual and will be replaced. Note: The IRB defines any individual that has signed an informed consent as an enrollment in this study and so screen failures should be reported to the IRB with enrollment numbers.
- On-Study: A subject is considered on-study on the date when the study team has confirmed the subject has met all of the inclusion and none of the exclusion criteria, and the treating physician/surgeon or study PI has signed off on the confirmation.
- On-Treatment: A subject is considered on-treatment on the date that they receive the first study treatment. A subject who is withdrawn or discontinues from the study after receiving at least 1 infusion is considered a discontinuation and will not be replaced.
- On Follow-up: A subject is considered on follow-up on the date that they have met any of the criteria in section 4.0.
- Off-Study: A subject is considered off-study if they are removed from the study for any of the reasons listed in section 4.0 or if they have completed all study assessments through follow-up.
- Immunologic Controls: A subject for whom biospecimen is obtained from the COVID-19 Biorepository.

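### Immunologic and PCR comparators have no stated severity, timing or co-treatment criteria matching the recipients', so secondary objective 3 is open to confounding of unknown direction and size

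*Combined protocol and SAP*

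**What the plan says.** **Recipients (Sections 4.1 and 4.2).** They enter within 72 hours of admission, outside the ICU and off high-flow oxygen. They may not be ventilated, on more than 6 L/min by nasal cannula, or in another COVID-19 treatment trial.

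**Immunologic controls (end of Section 4.5; also Summary and Section 10.9).** The cell-based inclusion rule is "PBMCs with 5-10 million cryopreserved cells per specimen with 2 timepoints per patient". The serum or plasma rule is a volume and two timepoints. The only exclusion is "Specimens not available through the COVID Repository protocol". Section 10.9 defines the group as "A subject for whom biospecimen is obtained from the COVID-19 Biorepository". Section 8.3 adds: "Immunologic Control samples from non-transfused hospitalized patients will be obtained from the UVA COVID-19 Biorepository". The Summary (Assessment and Data Acquisition, items 5 and 6) says control samples are assayed at two timepoints similar to the recipients'.

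**PCR comparators (Section 8.2).** "Trial patient samples will be compared to control non-transfused hospitalized patient samples stored in the clinical labs". No further criterion is given.

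**Clinical controls (Section 4.3).** The criteria are a floor-bed admission, no ventilation or flow above 6 L/min on admission, no other interventional treatment trial and no convalescent plasma. The heading says this group takes in control specimens.

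**Analysis (Section 9.1).** "These effects will be compared to biospecimen from non-transfused immunologic controls". Adjustment is planned, with age and comorbidity as examples. The analyses are called exploratory, without multiplicity adjustment, and a two-sided p below 0.05 counts as significant.

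**The concern.** Antibody titer, cytokines, T-cell phenotype and PCR positivity plausibly vary with severity, day of illness, and steroid or anti-cytokine treatment. Recipients are restricted on severity and time since admission at entry; the comparators, on their own list, are not. A difference between the groups, or the absence of one, could then reflect which inpatients have stored samples rather than plasma.

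Two things are at stake. One is secondary objective 3, which is this comparison. The other is the question in Section 5.6.2, whether passive antibody attenuates the patient's own immune response: comparators at another stage of illness could mimic or hide attenuation. The PCR comparison in Section 8.2 has the same weakness, but it uses a different specimen source and objective 3 does not name it.

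**Working it through.** **1. Criteria side by side**

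| Feature | Recipients (4.1, 4.2) | Immunologic controls (4.5, 8.3, 10.9, Summary) | PCR comparators (8.2) |
|---|---|---|---|
| Location | not ICU | hospitalized | hospitalized |
| Oxygen support | at most 6 L/min, not ventilated | none stated | none stated |
| Time since admission | within 72 hours | none stated | none stated |
| Time since symptom onset | none stated | none stated | none stated |
| Sampling days | fixed from infusion | two, similar to recipients' | none stated |
| Other treatment trials | excluded | none stated | none stated |
| Convalescent plasma | given | none | none |

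A control has no infusion, so the plan gives no day 0 from which a similar timepoint could be counted.

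**2. Does Section 4.3 close the gap?**

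- *If it does not govern specimens*, an ICU or ventilated inpatient qualifies as a comparator.
- *If it does*, the oxygen and ventilation limits apply on admission, not at sampling. A patient admitted to the floor and first sampled later, while ventilated, still qualifies. Section 4.3 has no 72-hour or symptom-onset window, and it excludes trial participation rather than immunomodulators given in routine care.

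The gap narrows on the second reading but stays open on both.

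**3. The plan's own figures.** Cell-based controls: 60 specimens / 2 timepoints = 30 patients. Serum or plasma: 50 patients × 2 = 100 specimens. Both agree with Section 2.3. No effect size or power is stated for this comparison; the 29-patient calculation concerns ICU admission only.

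**4. How much could case mix matter?** Illustration with assumed inputs: a marker with SD 1 in each group, no plasma effect, a fraction s of controls severe, and severe patients differing by D SD. The extra variance from mixing is ignored. Mean shift = s × D; SE = √(1/29 + 1/m); the noncentrality of the unadjusted two-sided t-test is s × D / SE.

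For m = 30, SE = √(0.03448 + 0.03333) = 0.260. For m = 50, SE = √(0.03448 + 0.02000) = 0.233.

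| s | D | Shift | P(p<0.05), 29 v 30 | P(p<0.05), 29 v 50 |
|---|---|---|---|---|
| 10% | 0.5 | 0.05 | 5.4% | 5.5% |
| 10% | 1 | 0.10 | 6.6% | 7.1% |
| 25% | 0.5 | 0.125 | 7.6% | 8.3% |
| 25% | 1 | 0.25 | 15.7% | 18.5% |
| 50% | 1 | 0.50 | 47.1% | 56.2% |

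The nominal value is 5%. The sign of D does not affect these probabilities.

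**5. Could needing two samples favour longer stays?** Again with assumed inputs: exponential stay with mean m0 without ICU care and m1 with it, a proportion π needing ICU care, and the second control sample taken in hospital on day d. The ICU share among those still in hospital is π·exp(−d/m1) / [π·exp(−d/m1) + (1−π)·exp(−d/m0)].

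Worked case, π = 0.5, m0 = 6, m1 = 16, d = 7: 0.5 × 0.646 / (0.5 × 0.646 + 0.5 × 0.311) = 67%.

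| π | m0, m1 (days) | Day 7 | Day 14 |
|---|---|---|---|
| 50% | 6, 16 | 67% | 81% |
| 25% | 6, 16 | 41% | 59% |
| 25% | 8, 16 | 34% | 44% |

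Sampling regardless of discharge would leave the share at π. In the treatment schedule, the recipients' antibody and immune-blood rows do not carry the footnote that stops daily assessments at discharge, though completeness after discharge is not described.

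**The case against.** **Section 4.3 may already cover this.** Clinical controls have no biospecimens collected prospectively, so stored specimens are a natural meaning for the heading, and the 4.5 list could be read as specimen requirements added to the 4.3 patient criteria. That reading is possible. But the Summary lists clinical and immunologic controls separately, each with its own criteria, and nothing in the text links the two. Even on that reading, the limits apply only on admission.

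**Timing and adjustment are not ignored.** This stands in part. Control samples are to be taken at similar timepoints, and the covariate list is open-ended. However, the timepoints have no anchor in a control, and severity, day of illness and co-treatment are not named.

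**The comparison is exploratory.** True, and it limits the consequences. It does not remove the bias, and the plan still applies a significance threshold.

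**The illustrations use no trial data.** This stands in full. The plan does not fix the day of the second control sample or say the patient was still admitted then. Section 8.2 also does not say why the stored swabs were taken. The repository's own protocol, which may carry entry rules, is not among the documents.

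A reader might infer that controls are chosen solely because specimens exist. They must also be untransfused and hospitalized, and the immunologic samples must fall at similar timepoints.

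**Conclusion.** The concern holds as a gap in the specification. Neither comparator set has a stated criterion on ICU status, oxygen support, time since admission or symptom onset, or co-treatment. Section 4.3 is unclear as to whether it fills the gap, and fills only part of it if it applies. Secondary objective 3 and, separately, the PCR comparison are therefore open to confounding by severity, day of illness and treatment.

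Its size is not knowable from the documents. Under the assumptions in step 4, the false-positive probability runs from essentially nominal (5.4%) to 56.2%, depending on an undescribed case mix. The length-of-stay figures show a possible mechanism, not an estimate.

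A reader might go further and infer that recipients are compared with a sicker, differently treated group. The documents do not establish that: the repository's case mix is not given, recipients may themselves receive steroids at the treating team's discretion (Section 5.2.3), and recipients may progress to the ICU during sampling. The direction of bias is unknown.

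The primary endpoints, the sample size and the decision rule are untouched. The change is worth making because it is cheap and the comparison is the whole of a stated objective.

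**What to change.** - **Reconcile 4.3 and 4.5.** State that the 4.3 patient-level criteria apply to both Biorepository and clinical-laboratory comparators, and must be met at the first sample: non-ICU, at most 6 L/min, within 72 hours of admission, not in another treatment trial. The 72-hour window is new to the controls and mirrors recipient entry.
- **Match.** Select control samples to match recipients on days since symptom onset (for example within 3 days) and baseline oxygen need. This also gives controls a time anchor.
- **Adjust.** Add severity, day of illness, and steroid or immunomodulator exposure before each sample to the Section 9.1 covariates.
- **PCR.** Compare results only within matched day-of-illness windows.
- **Report.** Criteria at the first sample do not remove selection by length of stay at the second. Give discharge and ICU status at the second sample in both groups, and describe the comparison as exploratory.

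Cost: an amendment to Sections 4.3, 4.5, 8.2, 8.3 and 9.1, and a chart look-up for each control. Fewer than 30 cell-based and 50 serum or plasma controls may qualify; the plan already allows fewer than 50 for serum. No stated figure for the primary endpoint changes.

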5.0 TREATMENT PLAN

5.1 Treatment Summary

The purpose of this study is to determine whether convalescent immune plasma infusion (CIP) can reduce ICU admissions, level of respirator support (oxygenation and ventilator support), and mortality. This is a single arm phase II trial to assess efficacy and confirm safety of infusions of anti-SARS-CoV-2 convalescent plasma in hospitalized patients with acute respiratory symptoms within 72 hours of admission with or without confirmed interstitial COVID-19 pneumonia by chest imaging. A total of 29 eligible subjects will be enrolled to receive high titer anti-SARS-CoV-2 plasma. We will document adverse events related to respiratory or clinical status on transfusion of SARS-CoV-2 convalescent plasma and serious adverse events during the study period: transfusion reaction (fever, rash), transfusion related acute lung injury (TRALI), transfusion associated circulatory overload (TACO), transfusion related infection, or electrolyte disturbances. Immune testing will be performed to sequentially profile the immune responses of the patients after they receive CIP. COVID-19 patients aged ≥ 18 years of age and respiratory symptoms within 72 hours of hospitalization will be enrolled in the study. Patients will receive 1-2 units (~200-400 mL) CIP with high titer plasma.

5.2 Study drug administration

- Drug will be administered in the hospital
- Infusion rate ≤ 500 mL/hour
- Pretreatment to minimize transfusion reactions (e.g. acetaminophen, diphenhydramine) may be given per investigator and clinical care team discretion.
- If an AE develops during infusion, the infusion may be slowed or stopped as per investigator's decision.
 - Most reactions to plasma are relatively minor and the infusion can generally be continued at a slower rate. Infusion site burning and non-allergic systemic effects can generally be managed with slowing of the infusion. Infusion can generally be continued in cases of itching or hives after pausing the transfusion, administering antihistamines, and observing the patient for worsening.
 - Severe allergic reactions such as bronchospasm and hypotension may require discontinuation of the infusion.

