5.6.3 Transfusion Transmitted Diseases

Finally, there are risks associated with any transfusion of plasma including transmission of transfusion transmitted viruses (e.g. HIV, HBV, HCV, etc.), allergic transfusion reactions, anaphylaxis to transfusion, febrile transfusion reaction, transfusion related acute lung injury (TRALI), transfusion-associated cardiac overload (TACO), and hemolysis should ABO incompatible plasma be administered. In order to minimize the risks of disease transmission, pathogen reduction techniques will be utilized to prepare the plasma. In addition, donors will fulfill all donor requirements for whole blood donation and frequent apheresis plasma donation with the exception of recent illness, in this case COVID-19 infection.

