15.0 STOPPING RULES

The study enrollment and dosing will be stopped and an ad hoc review will be performed if any of the specific following events occur or, if in the judgment of the study physician, subject safety is at risk of being compromised:

1. Death within one hour of plasma infusion
2. Occurrence of a life-threatening allergic/hypersensitivity reaction (anaphylaxis), manifested by bronchospasm with or without urticaria or angioedema requiring hemodynamic support with pressor medications or mechanical ventilation, TRALI, or TACO
3. One subject with a grade 4 or persistent grade 3 (≥ 72 hours) associated with study product.
4. Two subjects with persistent Grade 3 (≥ 72 hours) or higher lab toxicity for the same parameter associated with study product.
5. An overall pattern of symptomatic, clinical, or laboratory events that the medical monitor, ISM, or SMC consider associated with study product and that may appear minor in terms of individual events but that collectively may represent a serious potential concern for safety.
6. Any other event(s) which is considered to be a serious adverse event in the good clinical judgment of the attending physician team. This will be appropriately documented.

Upon completion of this review and receipt of the advice of the ISM or SMC, DMID will determine if study entry or study dosing should be interrupted or if study entry and study dosing may continue according to the protocol.

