15.1 Stopping Rules

Infusion of study drug will be halted if any of the following manifestations of anaphylaxis develop and will not be restarted:

- Skin or mucous membrane manifestations: hives, pruritus, flushing, swollen lips, tongue or uvula
- Respiratory compromise: dyspnea, wheezing, stridor, hypoxemia
- A decrease in systolic blood pressure to < 90 mmHg or >30% decrease from baseline or a diastolic drop of >30% from baseline.
- Tachycardia with an increase in resting heart rate to > 130bpm; or bradycardia <40 that is associated with dizziness, nausea or feeling faint.
- Any other symptom or sign which in the good clinical judgment of the study clinician or supervising physician warrants halting the infusion. For example, the rapid onset of gastrointestinal symptoms, such as nausea, vomiting, diarrhea, and cramps, for instance, may be manifestations of anaphylaxis and may warrant an immediate halt prior to meeting full SAE criteria

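### Hives or itching during infusion: section 5.2 lets the infusion resume after a pause, while section 15.1 lists the same signs, ungraded, under a rule that forbids restarting

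*Combined protocol and SAP*

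**What the plan says.** Section 5.2 (Study drug administration) leaves the response to an adverse event during infusion to the investigator: "If an AE develops during infusion, the infusion may be slowed or stopped". Among reactions it describes as mostly minor, it then says: "Infusion can generally be continued in cases of itching or hives after pausing the transfusion, administering antihistamines, and observing the patient for worsening". A separate bullet says that severe allergic reactions, with bronchospasm and hypotension as examples, may call for discontinuation.

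Section 15.1 (Stopping Rules) is mandatory: "Infusion of study drug will be halted if any of the following manifestations of anaphylaxis develop and will not be restarted". The first item under that rule is "Skin or mucous membrane manifestations: hives, pruritus, flushing, swollen lips, tongue or uvula". The next three items cover respiratory compromise, blood pressure and heart rate, and a fifth is a general clause left to clinical judgement.

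Section 15.0, item 2, which governs suspension of the whole study, describes anaphylaxis more narrowly, as a life-threatening reaction "manifested by bronchospasm with or without urticaria or angioedema requiring hemodynamic support with pressor medications or mechanical ventilation". Section 5.6.3 names these as separate risks of plasma: "allergic transfusion reactions, anaphylaxis to transfusion, febrile transfusion reaction".

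Sections 5.2 and 15.1 do not refer to each other.

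**The concern.** The same bedside event falls under two instructions. A clinician who pauses, gives antihistamines, observes and then resumes has followed section 5.2, but may have broken section 15.1. Two teams facing the same isolated skin reaction could act differently and each cite the protocol, and the volume infused could then differ between patients with the same reaction.

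Compliance is formally judged. Outside emergencies, section 17.2 requires the study to be run exactly as the approved protocol describes. Under section 16.2 the Data and Safety Monitoring Committee reviews how the stopping rules were applied and any protocol violations. As written, the committee has no text by which to classify a resumed infusion. The reaction is also one that the protocol expects: section 7.3.2 names rash among the transfusion reactions in a secondary safety endpoint.

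**Working it through.** The plan states no figure on this point and no formula applies. The check compares the sections.

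**1. Do the two rules name the same signs?**

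| | Section 5.2 | Section 15.1 |
|---|---|---|
| Skin signs named | itching, hives | hives, pruritus, flushing, swelling of lips, tongue or uvula |
| Force | permissive, qualified as the general case | mandatory |
| After a pause | may continue | may not restart |
| Severity condition on hives or itching | watch for worsening | none |

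Both signs in 5.2 (2 of 2) are in the 15.1 list, since pruritus is itching.

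**2. Does one sign suffice under 15.1?** Its opening sentence applies the rule if any listed manifestation develops. Read literally, one is enough. The skin item stands alone and requires no second sign.

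**3. Could a severity condition be implied?** The list shows that its authors set limits where they wanted them:

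- Blood pressure has three numeric limits: "A decrease in systolic blood pressure to < 90 mmHg or >30% decrease from baseline or a diastolic drop of >30% from baseline".
- Heart rate has two: above 130 and below 40. The lower one also needs a symptom: "bradycardia <40 that is associated with dizziness, nausea or feeling faint".
- Respiratory signs have none.
- Skin signs have none.

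So 2 of the 4 named sign groups carry limits, 3 + 2 = 5 limits in all. The fifth item is a judgement clause and is not counted. Hives and pruritus have no limit, grade, extent or accompanying sign.

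**4. Can the narrower description in 15.0 be read into 15.1?** Not comfortably. If bronchospasm were required, the separate skin item would have no role of its own. In its gastrointestinal example, 15.1 also contemplates stopping before full serious-adverse-event criteria are met, which points to an earlier trigger than the one in 15.0.

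**5. Which action is in conflict?** Stopping is allowed by 5.2 and required by 15.1, so it satisfies both. Resuming is allowed by 5.2 and, for a listed sign, forbidden by 15.1. The conflict is confined to resumption.

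**6. Is the mismatch isolated?** No. Section 5.2 says that bronchospasm and hypotension may call for discontinuation. Section 15.1 makes the halt mandatory for wheezing and for the defined falls in blood pressure. This suggests that the two sections were not harmonised.

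**The case against.** The strongest reply is that the sections describe two tiers. Section 15.1 is limited to manifestations of anaphylaxis. Section 5.2 places itching and hives with the minor reactions and treats severe allergic reactions in a separate bullet. Section 15.0 ties anaphylaxis to bronchospasm and the need for support, and section 5.6.3 lists allergic reactions and anaphylaxis separately. Section 5.2 is also permissive, so 15.1 can be read as limiting it. On this view the fault is an ambiguity rather than a contradiction.

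Much of this stands. The two-tier reading is plausible and may be what was meant. But the text does not secure it. Section 15.1 gives no test for when isolated hives or itching is a manifestation of anaphylaxis, and it makes any one listed sign sufficient. The general wording of 5.2 softens the conflict without removing it, because it still allows a resumption that 15.1 rules out.

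Two further objections are fair. First, the count of numeric limits is only supporting evidence: skin signs have no natural numeric threshold, and the respiratory group has no limit either. The overlap of signs carries the argument. Second, the consequences are limited. There are 29 planned recipients, and section 1.0 already allows a single unit where there are safety concerns, so a halt after the first unit leaves the patient within the permitted volume. A halt during the first unit would not. Section 17.2.2 gives criteria for deviations and violations, but does not settle whether resuming is one.

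**Conclusion.** The concern holds. As written, sections 5.2 and 15.1 give incompatible answers on whether an infusion may resume after hives or itching. The overlap is complete for the signs that 5.2 names (2 of 2), and the conflict is limited to resumption. The conclusion rests on the ordinary meaning of 15.1, under which any one listed sign triggers the rule. If the sponsor intended two tiers, the dividing line is missing from the protocol.

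The documents give no rate of skin reactions to plasma, so the number of patients affected is not estimated. The effect on the primary result is likely small. The matter should be corrected because it concerns infusion safety and the consistent classification of deviations.

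**What to change.** The sponsor's clinicians should reconcile sections 5.2 and 15.1, aligned with the description of anaphylaxis in section 15.0 item 2, into one instruction for hives and itching during infusion. Each section should cite the other. If two tiers are intended, the text should say so and state what separates them. The bronchospasm, wheezing and blood-pressure wording in the two sections should be checked in the same revision. Which clinical rule to adopt is for the sponsor's clinicians; this review takes no position on it.

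The cost is protocol wording and cross-references only.
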